# **B2. Evaluation Design**

The choice of a dynamic waitlisted design is based on WHS's plans for staged EBQI implementation at no more than eight VA facilities per year for the next three years for a total of 24 facilities. This randomized "roll-out" implementation design has very good statistical properties, including higher power than traditional

wait-listed designs and less vulnerability to external, uncontrolled factors. EBQI implementation will commence in Year 1 (FY17) in eight randomly selected facilities (Group 1), with the remaining 16 facilities serving as waitlisted controls. In FY18, eight of these waitlisted controls will be randomly selected for EBQI implementation (Group 2), leaving the remaining eight as waitlisted controls in FY18, which will begin EBQI implementation in Year 3 (Group 3).

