B4a. Key Stakeholders (KS). Semi-structured gualitative interviews will be conducted at baseline for all sites (Aim #1), as well as immediately prior to the EBQI launch of Groups 2 and 3. Interviews will be conducted at all sites at 12 months post-EBQI launch; in Group 1, interviews will also be conducted at 24 months. Sampling Plan: For Aim #1, we will work with the EBQI contractor to identify facility-level KS (e.g., quadrad member, PC director, WH medical director, WVPM, QI/system redesign lead; n~6/facility) and VISN-level KS (e.g., VISN director, VISN Lead WVPM, VISN system redesign lead; n~4/VISN). We will also interview WHS leaders and EBQI contractor personnel to evaluate leadership and implementation processes. We will adapt KS selection based on the QI targets established at initial EBQI site visits (e.g., add a MH director if the QI project targets MH). For Aim #3, we will seek to re-interview the same KS as in Aim #1, but will pursue replacement personnel in the event of turnover and/or position changes over time. Measures: The Aim #1 baseline interview guide (Appendix 3) includes guestions about the structure and delivery of usual care for WVs, barriers and facilitators to achieving delivery of comprehensive WH care, what (if any) improvements are underway in WH and/or for WVs, familiarity with performance metrics, access to metrics by gender, experience with QI, local culture, perceptions of the care environment, and engagement. The Aim #3 12- and 24-month interviews will assess any changes in care for WVs (staffing, structure, etc.), details of completed/in progress QI projects, perspectives on critical components of EBQI, and anticipated sustainability of local improvements and QI methods. Data Collection: Under the supervision of [name] (Co-PI), KS interviews will be conducted by telephone, recorded and professionally transcribed. Transcripts will be reviewed and edited for accuracy.

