In Q2, we will continue with KS interviews, including WHS and EBQI contractor interviews and extending the KS sample to accommodate EBQI targets in Group 1 (e.g., MH leads). We will update the provider/staff survey sample lists, and work with site-level evaluation contacts on sample validation and updated cover letters as needed (i.e., to accommodate leadership changes). By the end of Q2, we will deliver KS summaries and organizational survey findings. We will launch the second wave provider/staff surveys in Q2. We will also pull a second year of administrative data, and provide WHS with a summary report on changes.

In Q3, we will finish the provider/staff survey wave, clean the data and deliver an initial summary report. KS analysis will continue. KS contrasts between Year 1-2 will be reported, in addition to early findings regarding Aim #3 contextual factors and implementation processes based on both waves. Additional organizational analyses with linked administrative data for Aim #2 will also be reported (e.g., variations in resource sufficiency by large and small low-performers).

In Q4, organizational changes based on KS interviews and organizational surveys between Years 1 and 2 overall and by EBQI vs. waitlisted controls will be reported to WHS. We will deliver a second annual report for WHS, summarizing findings across evaluation data sources for FY18, with notable FY17 comparisons.

**FY19**: In Q1, the EBQI contractor will launch EBQI in the remaining low-performing VA facilities. We will again update the KS sample as needed, and launch the third and final wave of KS interviews and again

extend the KS sample to accommodate EBQI targets in Groups 1 and 2 that will have had two and one year of EBQI, respectively. We will start with the baseline KS interviews for Group 3, followed by the KS followup interviews for Groups 1 and 2, which may carry over into Q2. We will again repeat OASC and Union review, and launch the third and final organizational survey wave.

In Q2, we will complete the KS interviews, and initiate rapid KS analysis. We will update the provider/staff sample for the third wave, repeat sample validation steps with participating sites, and prepare endorsement letters once again, and launch the survey by the end of Q2. By the end of Q2, we will also provide WHS with the third wave of KS summaries and an organizational survey summary in the quarterly report.

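### The FY18 EBQI vs waitlist contrast of organizational change from key stakeholder interviews has no follow-up in Group 3, and it ascertains change unequally against Group 2, the only usable comparator

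*Combined protocol and SAP*

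**What the plan says.** Section D2 (FY18 Q4) states that "organizational changes based on KS interviews and organizational surveys between Years 1 and 2 overall and by EBQI vs. waitlisted controls will be reported". Interviews are thus to be one basis for a between-arm comparison of change.

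Section B2 defines the arms. Group 1 starts EBQI in FY17 and Group 2 in FY18, "leaving the remaining eight as waitlisted controls in FY18" (these are Group 3).

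Section B4a sets the interview schedule. All sites are interviewed at baseline, "as well as immediately prior to the EBQI launch of Groups 2 and 3". After that, timing runs from each site's own launch: "Interviews will be conducted at all sites at 12 months post-EBQI launch; in Group 1, interviews will also be conducted at 24 months".

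B4a also describes two guides. The baseline guide covers usual care, barriers and facilitators, QI experience, and any improvements in progress. By contrast, the "12- and 24-month interviews will assess any changes in care for WVs (staffing, structure, etc.), details of completed/in progress QI projects", together with views on EBQI components and sustainability.

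On informants, B4a plans about six per facility and adds: "We will adapt KS selection based on the QI targets established at initial EBQI site visits". The FY18 Q2 entry in D2 applies this to Group 1, with mental health leads as the example.

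**The concern.** A comparison of change between arms needs a before and an after measurement in both arms, taken in much the same way. Here one control group seems to have no after measurement in the reporting window. The other seems to be measured with a different guide and a narrower set of informants.

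If change is sought harder at EBQI sites, more of it may be recorded there even when both arms changed equally. The report goes to the partner running the rollout, at the end of FY18 and just before the last eight launches. Section B5b itself calls 24 sites a small sample for site-level effects, so a persuasive interview contrast could carry weight.

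**Working it through.** The documents state no sample size, effect size or error rate for this contrast, so there is no figure to reproduce. The check sets the passages side by side.

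**Step 1: interview rounds by group and year** (from B2, B4a, and the FY17 to FY19 entries in D2).

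| Group | FY17 | FY18 | FY19 |
|---|---|---|---|
| 1 | baseline | 12 months post-launch | 24 months post-launch |
| 2 | baseline | pre-launch (Q1) | 12 months post-launch |
| 3 | baseline | none scheduled | pre-launch (Q1) |

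At about 6 facility-level informants per site, each round is about 8 × 6 = 48 interviews. In FY18 that gives about 48 in Group 1 (before additions), about 48 in Group 2 and none scheduled in Group 3. Group 3's second interview falls in FY19 Q1, after the FY18 Q4 report.

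**Step 2: what can be compared.** Group 1 vs Group 3 has no Year 2 interview on the control side, so that contrast cannot be estimated. Group 1 vs Group 2 pre-launch can be formed, because Group 2 was waitlisted throughout FY17 and is interviewed again before it launches. D2 does not say which group is meant by the waitlisted controls.

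**Step 3: is that comparison like for like?**
- *Guide.* Group 1 gets the 12-month guide. D2 (FY18 Q1) labels Group 2's interview baseline, so the baseline guide is presumably used. As described, that guide asks about improvements underway, but it lists no question on what has changed since the last interview and no account of completed projects.
- *Informants.* Additions follow QI targets set at EBQI site visits. A site that has not launched has no such targets, so it gets no equivalent additions.

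Both differences coincide with EBQI exposure.

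**Step 4: illustration of the mechanism only.** Suppose a site counts as changed if at least one of k informants mentions a change, and that mentions are independent with probability p. Then P = 1 − (1 − p)^k. The counting rule, the independence and every rate below are assumptions. True change is taken as equal in both arms.

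- One added informant (7 vs 6), same guide, p = 0.10: 1 − 0.9^7 = 0.522 vs 1 − 0.9^6 = 0.469, a gap of 5.3 points. Over p = 0.05, 0.10, 0.20 and 0.30 the gap is 3.5 to 5.3 points.
- The same, with the pre-launch guide drawing 75% as many mentions: 9.7 to 16.7 points.
- The same, at 50% as many mentions: 16.1 to 32.2 points.

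The spread from 3.5 to 32.2 points shows that the size depends on rates the documents do not give.

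**The case against.** The strongest reply is that the interviews are not an effectiveness measure. Sections B1 and B5a assign them to Aims #1 and #3. Section B5b builds the Aim #2 models on organizational surveys, provider/staff surveys and administrative data. The FY18 Q4 item is one interim report, and it also uses surveys planned for all 24 sites. This stands and limits the consequence.

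The reply also corrects several stronger readings that a reader might infer:

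- *That the contrast must favour EBQI.* The missing Group 3 round makes a contrast impossible; it does not push it in a direction. For Group 2, B5a looks for factors that impeded EBQI as well as those that helped, and added informants may report problems. No counting rule is given. A direction is likely, not established.
- *That waitlist sites are never asked about change.* The baseline guide does ask about improvements in progress. The difference is one of depth and reference period. The guide (Appendix 3) is not in the text reviewed, D2 describes it as a draft still to be reviewed with the partner, and its use before launch is inferred from a label.
- *That no waitlist comparator exists.* Group 2 before launch is one.
- *That the distortion is large.* Assumed mention rates of 0.30 and 0.10 with six informants each would give 88% vs 47% of sites, but nothing in the documents supports those rates.

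Two further arguments only partly succeed. D2's description of the second interview wave is not an exhaustive list, so Group 3 interviews are not excluded; however, none is scheduled. Matrices by role (B5a) would let added informants be separated and successive descriptions of a site be compared, but the plan does not commit to doing either for this contrast.

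**Conclusion.** The concern holds in a limited form. As scheduled, an interview-based Year 1-2 contrast with Group 3 cannot be estimated. The contrast with Group 2 pre-launch can be formed, but change is ascertained unequally: Group 1 gets deeper questions on change and extra informants from the domain being worked on. This is likely, not certain, to favour EBQI, and its size is unknown.

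The conclusion assumes that Group 2's pre-launch interview uses the baseline guide as B4a describes it, and that no unscheduled FY18 round takes place in Group 3. It does not extend to the Aim #2 effectiveness estimates, which use no interview data. The point is worth acting on because the correction is cheap and the report reaches the partner while the rollout is under way.

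**What to change.** **In B4a:** add one short block on changes in care and QI projects since the last interview to the pre-launch interviews of Groups 2 and 3, worded exactly as in the 12-month guide.

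**In D2 (FY18 Q4):** define the Year 1-2 interview contrast as Group 1 at 12 months vs Group 2 pre-launch, restricted to the core roles interviewed at every site. State that Group 3 does not contribute interview data to this report and that its FY19 Q1 pre-launch interview serves as the later waitlist comparator. Use target-specific added informants only for the Aim #3 process description.

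**If the block is not added:** take the interviews out of the EBQI vs waitlist report and base it on organizational survey items asked identically at all 24 sites. Exclude the domains that B4b allows to be adapted to EBQI targets in Years 2 and 3, since otherwise a similar imbalance could enter through the surveys.

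**Cost:** a few minutes of each 30-minute pre-launch interview (the length planned in B6c) and a line or two of text. No extra interviews are needed. A Group 3 round in FY18 would close the remaining gap directly, at about 8 × 6 = 48 further interviews, but the correction above does not depend on it.
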